4 INVESTIGATIONAL PLAN

4.1 Overall Study Design and Plan

This is a Phase 3, global, multicenter study that will evaluate subjects with moderately to severely active PsA. The subject population will consist of no more than 50% with a demonstrated inadequate response (lack of efficacy after a minimum 12 week duration of therapy) or intolerance to 1 or 2 biologic therapies (Bio IR). The remaining study population will be subjects who have had an inadequate response (lack of efficacy after a minimum 12 week duration of therapy) or intolerance to at least 1 csDMARD.

The study consists of a Screening Period (approximately 35 days), Period 1, Period 2, and a 20-week Follow-up Period ([Figure 1](#)). Period 1 is a 24-week randomized, double-blind, placebo-controlled, parallel-group period. Period 2 starts at Week 24. To maintain the blind to the original treatment allocation, treatment at the Week 24 Visit will be blinded: subjects randomized to placebo will receive blinded risankizumab 150 mg, and subjects randomized to risankizumab will receive blinded placebo. At Week 28 and for the remaining dosing visits (to Week 208), all subjects will receive open-label risankizumab 150 mg q12w. Subjects will remain blinded to the original randomization allocation for the duration of the study. The total study duration is 228 weeks including a telephone call 140 days (20 weeks) after last dose of study drug.

Screening Period

Subjects will be screened for eligibility to enroll in the study until approximately 420 subjects (210/arm) have been randomized. Once 420 subjects have been randomized, subjects who have started screening but not yet been randomized will be allowed to enroll in the study if eligible. No further subjects will be

screened once sufficient numbers of subjects to fulfill the enrollment target have entered the screening process.

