8.0 Efficacy Analyses

8.1 General Considerations

All efficacy analyses will be conducted in the FAS Population. In addition, Per-protocol analysis for primary endpoint will be performed. All tests will be 2-sided at an alpha level of 0.05.

The Primary Analysis will be conducted after all ongoing subjects have completed Week 24 and the Week-24 Database Lock has occurred. Efficacy and safety analyses will be performed for Period 1 and long-term efficacy and safety will be summarized through the data cutoff date. An additional interim database lock will be conducted to provide further efficacy and safety exposure for integrated summaries of efficacy and safety supporting the initial regulatory submission; no study-specific analysis will be performed based on this database lock.

Unless otherwise specified, categorical variables will be analyzed using Cochran-Mantel-Haenszel (CMH) test, adjusting for the stratification factors. Continuous variables will be analyzed using Mixed-Effect Model Repeat Measurement (MMRM) method.

Unless otherwise specified, any subject who is randomized based on a wrong stratum will be analyzed according to the actual stratum the subject belongs to.

"Baseline" refers to the last non-missing observation before the first administration of study drug or before randomization if no study drug is given.

Efficacy analysis for Period 1

The efficacy analysis for Period 1 will be performed after all ongoing subjects have completed Period 1 and an interim database lock has occurred. This is the only and final efficacy analysis in Period 1.

Long-term efficacy analysis

Long-term efficacy will be summarized based on data in Period 1 and Period 2 up to data cutoff date for the Week-24 Database Lock. After the initial regulatory submission, additional interim analyses will be performed as deemed appropriate, for example, to address requests from regulatory agencies. The final analysis will be performed after all ongoing subjects complete the study.

The long-term efficacy analysis will be performed on As Observed data (defined in Section 8.2) by randomized treatment group sequence as described below:

1. Placebo → risankizumab 150 mg
2. risankizumab 150 mg → risankizumab 150 mg

There will be no statistical testing for long-term efficacy analysis; only descriptive statistics and 95% confidence intervals will be provided.

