9.0 Safety Analyses

9.1 General Considerations

Safety data will be summarized for the safety population. For the safety analysis, subjects are assigned to a treatment group based on the treatment actually received, regardless of the treatment randomized. A subject's actual treatment will be determined by the most frequent dose regimen received.

There are two sets of planned safety analysis: safety analysis for Period 1, and long-term safety analysis.

Safety Analysis for Period 1

Standard safety analysis by the actual treatment groups of risankizumab 150 mg and placebo will be performed on safety data up to Week 24. No protocol-defined treatment switching will occur prior to these time points.

The standard safety analyses will include reporting of adverse events (AEs), laboratory, and vital signs measurements. Frequency tables of subjects with treatment-emergent adverse events (TEAEs) by system organ class (SOC) and by preferred term (PT) as in the Medical Dictionary for Regulatory Activities (MedDRA) dictionary will be provided by treatment group. All continuous laboratory parameters and vital signs variables at each visit will also be summarized by actual treatment group. Frequency tables of subjects meeting criteria for potentially clinically significant vital sign values and for potentially clinically significant laboratory values will be provided by treatment group.

Long-Term Safety Analysis

Long-term safety analysis will be performed on all cumulative safety data in Period 1 and Period 2 up to data cutoff date for any interim lock as deemed appropriate and final lock. Long-term safety analyses that account for protocol-defined treatment switching include reporting of AE rate adjusted by cumulative exposure, descriptive summary in laboratory parameters and vital sign variables, and rate of potentially clinically significant laboratory and vital signs values.

To adjust for potentially different follow-up time between treatment groups, exposure-adjusted event rate (EAER) will be provided for long term safety analysis. The EAER will be presented for Any Risankizumab group by actual treatment received at the time of AE. The Any Risankizumab group includes all subjects who received risankisumab 150 mg, including those who started on risankizumab 150 mg at randomization and who switched from placebo to risankizumab 150 mg.

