For EAER calculation, the numerator will be the total number of AEs reported for the event (i.e., a subject can contribute more than one event to the numerator) and the denominator will be the total exposure time among subjects under the treatment group. The number of AEs reported (numerator), the total number of years of study drug exposure (denominator, calculated as total number of days exposed to study drug (i.e., last dose date – first dose date + 140 days) for all treated subjects divided by 365.25), and the exposure-adjusted AE event rate per 100 patient-years calculated as $(\text{[numerator (number of AEs)/denominator]}) \cdot 100$ will be presented for each treatment group.

All continuous laboratory parameters and vital signs variables at each visit will be summarized by actual treatment group sequence defined as follows.

1. Placebo → Risankizumab 150 mg
2. Risankizumab 150 mg → Risankizumab 150 mg

Frequency tables and listings of subjects meeting criteria for potentially clinically significant vital sign values and for potentially clinically significant laboratory values will be provided for Any Risankizumab group by actual treatment received at the time of event. Missing safety data will not be imputed.

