9.2 Adverse Events

A treatment-emergent Adverse Event (TEAE) is defined as an adverse event with an onset date that is after the first dose of study drug, and no more than 140 days after the last dose of study drug.

Adverse events (AEs) will be summarized and presented using primary MedDRA System Organ Classes (SOCs) and preferred terms (PTs) according to the version of the MedDRA coding dictionary used for the study at the time of database lock. The actual version of the MedDRA coding dictionary used will be noted in the AE tables and in the clinical study report. Specific adverse events will be counted once for each subject for calculating percentages, unless stated otherwise. In addition, if the same adverse event occurs

multiple times within a subject, the highest severity and level of relationship to investigational product will be reported.

9.2.1 Analysis of Adverse Events for Period 1

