9.2.1.1 Adverse Event Overview

An overview of AEs will be presented consisting of the number and percentage of subjects experiencing at least one event for each of the following AE categories:

- Any TEAEs
- Any COVID-19 related TEAEs
- Any TEAE related to study drug according to the investigator
- Any serious TEAE
- Any severe TEAE
- Any TEAE leading to discontinuation of study drug
- Any TEAE leading to death
- All deaths
 - COVID-19 related deaths
 - Deaths occurring \leq 140 days after last dose of study drug
 - Deaths occurring $>$ 140 days after last dose of study drug.

Additional AEs may be considered for tabulation/summary based on recommendations from Clinical and Safety as deemed appropriate.

The number and percentage of subjects experiencing at least one event of treatment-emergent AEs will be summarized for each treatment group. The point estimate and 95% CI (using normal approximation and separate group variance) will be provided for the treatment difference in AE percentage between risankizumab group and the placebo group. An overview of the AE of safety interest (ASI) will be provided similarly and the categories of ASI is defined in Section 9.2.1.4. In addition, an overview of AEs per 100 patient-years of study exposure will be presented for the AE categories defined

above. The number of TEAEs reported, the total number of years of study drug exposure, and the TEAE rate per 100 patient-years will be presented.

COVID-19 cases will be identified using relevant terms for COVID-19 search available in MedDRA version 23.0 or higher. All COVID-19 related AEs and COVID-19 related deaths will be summarized in the TEAE Overview table.

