9.2.1.4 Frequent ($\geq 1\%$) Adverse Events by Preferred Term in Decreasing Frequency

TEAEs occurring for at least 1% of the subjects in any of the treatment arms will be summarized by MedDRA PT in decreasing frequency of Risankizumab treatment group.

Areas of Safety Interest

The Adverse Events of Safety Interest (ASI) categories will be summarized by SOC and PT and will be based on standardized or company MedDRA queries (SMQs or CMQs). ASI are categorized in [Appendix B](#). Adjudicated cardiovascular events will be summarized and presented by treatment group using the CAC adjudicated categories. Serious opportunistic infection excluding tuberculosis and herpes zoster, serious hypersensitivity, serious hepatic events and serious injection site reaction will also be summarized by PT.

In addition, an overview of ASI per 100 patient-years of study exposure will be presented. The number of TEAEs reported, the total number of years of study drug exposure, and the TEAE rate per 100 patient-years will be presented.

Similarly, overview tables for serious ASI in number and percentage as well as in event rate per 100 patient-years will be provided.

Additional AEs may be considered for tabulation/summary based on recommendations from Clinical and Safety teams, as deemed appropriate.

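### The adverse-event rate denominator adds 140 days after the last dose with no cap at Week 24 or the data cut-off, so absolute rates at the Week-24 and later interim locks are biased low

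*SAP*

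**What the plan says.** SAP 9.1 takes the number of adverse events as the numerator of the exposure-adjusted rate and study-drug exposure as the denominator. It calculates total days as "last dose date – first dose date + 140 days) for all treated subjects divided by 365.25". No other term shortens a subject's contribution.

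The same section bounds the data. The double-blind part is limited as follows: "Standard safety analysis by the actual treatment groups of risankizumab 150 mg and placebo will be performed on safety data up to Week 24". For the long term: "Long-term safety analysis will be performed on all cumulative safety data in Period 1 and Period 2 up to data cutoff date". SAP 8.1 adds that at the Week-24 lock "long-term efficacy and safety will be summarized through the data cutoff date". SAP 2.2 says that lock supports the initial regulatory submission.

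SAP 9.2 counts an event as treatment-emergent if it starts after the first dose and "no more than 140 days after the last dose of study drug". This is evidently where the 140-day tail comes from.

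Rates per 100 patient-years are also required for Period 1. SAP 9.2.1.1 says "an overview of AEs per 100 patient-years of study exposure will be presented for the AE categories defined", and SAP 9.2.1.4 asks for the same for events of safety interest: "the total number of years of study drug exposure, and the TEAE rate per 100 patient-years will be presented". Neither section defines exposure. SAP 6.0 has a separate treatment duration, last dose minus first dose plus 84 days, also uncapped and not described as a rate denominator.

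**The concern.** A rate is interpretable only if its denominator covers the time during which its events could be counted. Here the event count stops at Week 24 or the cut-off, while the denominator can run up to 140 days further. In Period 1 the surplus days in the placebo arm would also fall after those subjects have switched to risankizumab.

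The error always makes rates look lower. It is largest at the Week-24 lock, when follow-up is shortest and the results go into the submission. The long-term rates are shown only for the Any Risankizumab group, so there is no concurrent arm carrying the same error against which to read them. Rates of serious infection, major cardiovascular events and malignancy would be among those affected.

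**Working it through.** The plan states no patient-year total or event rate, so there is no figure to reproduce. The check compares credited with observed time.

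**Inputs**
- Period 1 doses at Weeks 0, 4 and 16; Period 2 doses at Weeks 24 and 28, then every 12 weeks to Week 208 (Protocol 4.1).
- 210 subjects per arm, allocated 1:1 (Protocol 5.8).
- Tail of 140 days (SAP 9.1); alternative tail of 84 days (SAP 6.0).
- Enrolment period, mean exposure at the lock and dropout at the lock are not given, so the values below are assumed.

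**Formulas.** With F the first dose, L the last dose and C the end of counted data:
- credited time D = L − F + 140
- observed time R = min(L + 140, C) − F
- understatement of the rate = 1 − R/D

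**Final lock.** Week 208 is day 1456, and 1456 + 140 = 1596 = 228 × 7. Protocol 4.1 agrees: "The total study duration is 228 weeks including a telephone call 140 days (20 weeks) after last dose of study drug". Credited and observed time coincide for completers, so there is no bias for them.

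**Period 1, if the 9.1 formula applies**
- All three doses: D = 112 + 140 = 252 days; R = 168 days; 1 − 168/252 = 33.3%.
- Per 210 subjects: 210 × 252/365.25 = 144.9 patient-years credited, against 210 × 168/365.25 = 96.6 observed.
- Last dose at Week 0 or Week 4: D = 140 or 168 days, which does not pass Week 24, so there is no excess if the subject is followed.
- 5% stopping that early (assumed): 32.2% to 32.4%. 15% stopping: 29.8% to 30.4%.
- With the 84-day tail instead: D = 112 + 84 = 196 days; 1 − 168/196 = 14.3%.

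**Long term, one ongoing subject dosed every 12 weeks.** At cut-off, 0 to 84 days have passed since the last dose. The excess is therefore 140 − 84 = 56 to 140 days, on average 140 − 42 = 98 days = 0.268 years. A placebo subject cut off just before the Week 28 dose has had one risankizumab dose and is credited 140 days for 28 observed.

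For a mean observed exposure of t years the understatement is 0.268/(t + 0.268): 35% for t = 0.5, 21% for t = 1, 12% for t = 2.

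**Any Risankizumab at the Week-24 lock.** Assume 1:1 allocation, uniform enrolment, no dropout, and cut-off when the last subject reaches Week 24. With enrolment over E weeks, mean observed time is (24 + E/2) weeks in the risankizumab arm and E/2 weeks after the switch in the placebo arm. Credited time follows the actual dosing dates. Percentages are from unrounded values.

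| Enrolment (weeks) | Observed, mean years | Credited, mean years | Rate too low by |
|---|---|---|---|
| 26 | 0.479 | 0.755 | 36.5% |
| 52 | 0.728 | 0.997 | 26.9% |
| 78 | 0.977 | 1.248 | 21.7% |
| 104 | 1.227 | 1.498 | 18.1% |

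Allowing 10% to stop dosing by Week 24 at a constant hazard, with follow-up continuing (assumed), gives about 35%, 25%, 20% and 16%.

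**The case against.** The strongest objection concerns Period 1. The formula sits under the long-term heading of SAP 9.1, and 9.2.1.1 and 9.2.1.4 do not refer back to it. SAP 9.1 also describes the denominator as exposure of subjects under the treatment group, and time after the Week 24 switch is not time under placebo. The 252-day figure further takes the last dose to be the Week 16 dose.

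Part of this stands: the Period 1 application is an inference, and 33% is conditional on it. But the Period 1 sections use the same exposure term that 9.1 defines, and no other definition is offered. The only other candidate, in SAP 6.0, also overshoots Week 24. Taking the Week 24 dose as the last dose makes matters worse: 168 + 140 = 308 days credited, 1 − 168/308 = 45%.

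For the long-term rates, it can be said that a programmer would apply the cut-off to exposure as a matter of course. The SAP does not say so, and its explicit formula says otherwise.

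Three limits on scope are fair. The second planned interim lock yields no study-specific analysis, and later locks are optional, so the definite exposure is the long-term summary at the Week-24 lock. Dropout lowers the table's figures by about two percentage points. Finally, no test or decision rule rests on these rates: the planned Period 1 comparison is the difference in percentages with a confidence interval, which does not use the denominator.

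**Conclusion.** The concern holds. As written, the denominator counts time beyond the point at which events stop being counted, and absolute rates per 100 patient-years are too low at every lock before the 140-day tail has been observed.

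- **Long-term rates at the Week-24 lock:** too low by about 18% to 37% for enrolment over 104 down to 26 weeks with no dropout. The size depends on assumed enrolment; the direction does not. This part follows directly from the stated formula.
- **Period 1 rates:** too low by 33% if the 9.1 formula governs (30% to 32% with 5% to 15% early stopping), or 14% under the 84-day definition. This part rests on an inference, because the SAP leaves the Period 1 denominator undefined.
- **Not affected:** percentages of subjects with events and their confidence intervals, and completers at the final lock. Period 1 rate ratios barely move if discontinuation is similar between arms.

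No efficacy conclusion is touched. It should still be fixed, because descriptive safety rates supporting a submission would be systematically favourable to the drug.

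**What to change.** Add to SAP 9.1 that each subject's exposure ends at the earliest of: last dose plus 140 days; Week 24 or the first Period 2 dose (Period 1 analyses only); the data cut-off; death; and end of study participation. State that this definition also supplies the denominator for the Period 1 rates in 9.2.1.1 and 9.2.1.4. State outright that Any Risankizumab time starts at the first risankizumab dose, which 9.1 and 9.2.2 already imply.

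The cost is a short SAP amendment and one programming rule. Final-lock results for completers do not change. Rates at the Week-24 and any later interim locks will look less favourable than under the uncapped formula.

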9.2 Adverse Events

A treatment-emergent Adverse Event (TEAE) is defined as an adverse event with an onset date that is after the first dose of study drug, and no more than 140 days after the last dose of study drug.

Adverse events (AEs) will be summarized and presented using primary MedDRA System Organ Classes (SOCs) and preferred terms (PTs) according to the version of the MedDRA coding dictionary used for the study at the time of database lock. The actual version of the MedDRA coding dictionary used will be noted in the AE tables and in the clinical study report. Specific adverse events will be counted once for each subject for calculating percentages, unless stated otherwise. In addition, if the same adverse event occurs

multiple times within a subject, the highest severity and level of relationship to investigational product will be reported.

9.2.1 Analysis of Adverse Events for Period 1

9.2.1.1 Adverse Event Overview

An overview of AEs will be presented consisting of the number and percentage of subjects experiencing at least one event for each of the following AE categories:

- Any TEAEs
- Any COVID-19 related TEAEs
- Any TEAE related to study drug according to the investigator
- Any serious TEAE
- Any severe TEAE
- Any TEAE leading to discontinuation of study drug
- Any TEAE leading to death
- All deaths
 - COVID-19 related deaths
 - Deaths occurring \leq 140 days after last dose of study drug
 - Deaths occurring $>$ 140 days after last dose of study drug.

Additional AEs may be considered for tabulation/summary based on recommendations from Clinical and Safety as deemed appropriate.

The number and percentage of subjects experiencing at least one event of treatment-emergent AEs will be summarized for each treatment group. The point estimate and 95% CI (using normal approximation and separate group variance) will be provided for the treatment difference in AE percentage between risankizumab group and the placebo group. An overview of the AE of safety interest (ASI) will be provided similarly and the categories of ASI is defined in Section 9.2.1.4. In addition, an overview of AEs per 100 patient-years of study exposure will be presented for the AE categories defined

above. The number of TEAEs reported, the total number of years of study drug exposure, and the TEAE rate per 100 patient-years will be presented.

COVID-19 cases will be identified using relevant terms for COVID-19 search available in MedDRA version 23.0 or higher. All COVID-19 related AEs and COVID-19 related deaths will be summarized in the TEAE Overview table.

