As of 29 March 2018, 2,471 subjects in the psoriasis studies were exposed to ≥ 1 dose of risankizumab at any dosage level (including subjects who received placebo for Weeks 0 to 16 and then switched to risankizumab), representing 3,352 patient years (PYs) of exposure. Of the 2,471 subjects, 1,671 have had exposure to risankizumab at any dosage for at least 1 year. In the pivotal global Phase 3 plaque psoriasis studies, over the initial 16 weeks of exposure, the frequencies of adverse events (AEs) were similar in subjects treated with risankizumab (48.9%) compared to placebo (48.3%). Through Week 52, the exposure-adjusted rate of AEs in subjects in the risankizumab group was comparable to the event rate in the ustekinumab group (228.0 E/100 PYs in the risankizumab group and 281.0 E/100 PYs in the ustekinumab group). Likewise, serious adverse events per 100 subject-years were 9.4 for subjects treated with risankizumab and 10.9 for those treated with ustekinumab. Approximately 2.0% of subjects discontinued due to AEs. Few subjects had AEs in the following areas of safety interest: major adverse cardiac events (MACE), infections, malignancies, hepatic events, injection site events, or hypersensitivity reactions.

The Phase 2 program in PsA with risankizumab demonstrated efficacy for improvement in signs and symptoms of PsA and the safety results were consistent with those known to be associated with IL-23 antagonists. Taken together, the safety and efficacy data from the Phase 2 program support further development of risankizumab in Phase 3 in subjects with PsA.

Although rare, a potential for hepatic AEs is under constant surveillance by sponsors and regulators. Therefore, this study requires timely detection, evaluation, and follow-up of laboratory alterations in selected liver laboratory parameters to ensure subjects' safety.

Increases in major adverse cardiovascular events (MACE), including myocardial infarction (MI), cerebrovascular accident, and cardiovascular death, reported initially with anti-IL-12/23 agents, such as ustekinumab, have not been observed in longer term studies. While the likelihood of increased MACE is small, all suspected cardiovascular events (serious or nonserious) observed in this study will be adjudicated by an independent committee. An independent Cardiovascular Adjudication Committee (CAC) will adjudicate all observed cardio- and cerebro-vascular events and will remain blinded to treatment allocation (Section 6.4).

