2.4 Sample Size Determination

Approximately 420 subjects will be randomized to risankizumab 150 mg or placebo in a ratio of 1:1 (210 subject/treatment group). A sample size of 210 in each group will have approximately 90% power to detect a difference in HAQ-DI mean change from baseline of 0.24 assuming that the common standard deviation is 0.72 using a two group t-test with a 0.05 two-sided significance level and accounting for a 10% dropout rate. This sample size also ensures that analyses will have at least a 90% power to detect a 20% treatment difference, with the placebo response rate seen in the previous Phase 2b study of 35.7%, in ACR20 at Week 24 using a two-sided test at a 0.05 significance level and accounting for a 10% dropout rate.

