9.3.2.1 Assessment of Mean Change from Baseline in Clinical Laboratory Variables

Analyses of key continuous hematology and chemistry variables which are measured longitudinally will be performed by visits and by treatment group. For each parameter at each visit, the following summary statistics will be presented for each treatment group: sample size, mean, standard deviation, minimum, median and maximum.

An ANOVA model with treatment as a factor will be used to compare change from baseline between different treatment groups for selected laboratory parameters. Mean difference from placebo and associated 95% CIs will be presented. The analysis applies to the following laboratory parameters of clinical interest

- Hematology parameters: WBC, neutrophils, lymphocytes, RBC, hematocrit, hemoglobin, platelets count.
- Chemistry parameters: total bilirubin, GGT, ALP, SGOT/AST, SGPT/ALT, glucose, creatinine, potassium, sodium, calcium.

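### Period 1 safety intervals: the Wald interval for adverse-event differences collapses for rare events, and the laboratory comparison leaves out the baseline covariate

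*SAP*

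**What the plan says.** SAP 9.2.1.1 sets the method for the difference in adverse-event percentages between the arms in Period 1: "95% CI (using normal approximation and separate group variance) will be provided for the treatment difference in AE percentage". A normal approximation with a separate variance for each group is the unpooled Wald interval. The section continues: "An overview of the AE of safety interest (ASI) will be provided similarly". SAP Appendix B lists these events. They include adjudicated MACE, active tuberculosis, opportunistic infection, malignant tumours, and serious and adjudicated anaphylactic reactions. The adverse-event overview itself contains deaths and fatal adverse events. No exact, score or corrected interval is named for small counts.

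SAP 9.2.1.5 asks for the same difference and 95% interval within groups defined by prior biologic use, and names no method.

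For laboratory values, SAP 9.3.2.1 states: "An ANOVA model with treatment as a factor will be used to compare change from baseline between different treatment groups". Treatment is the only term. In contrast, the SAP's models for continuous efficacy endpoints (MMRM in 8.2, ANCOVA in 8.4.2) include the baseline value as a covariate.

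**The concern.** The Wald standard error is computed from the observed proportions. When an arm has no events, its estimated variance is zero. With no events in either arm the interval has no width, so the table claims exact knowledge of no difference where the trial has least information. With one to three events it is too short.

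These are realistic counts. The Protocol says of the psoriasis programme: "Few subjects had AEs in the following areas of safety interest: major adverse cardiac events (MACE), infections, malignancies, hepatic events". Comparing safety with placebo is a stated secondary objective, and Period 1 is the only randomised safety comparison, because every continuing subject receives risankizumab in Period 2. A reader who takes the upper limit as the largest excess risk compatible with the data would be falsely reassured.

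The laboratory issue runs the other way. Subtracting baseline without also adjusting for it gives a valid interval that is wider than necessary. It also leaves part of any chance baseline imbalance in the estimated drug effect.

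**Working it through.** **Inputs.** SAP 2.4 gives the arm size: "Approximately 420 subjects will be randomized to risankizumab 150 mg or placebo in a ratio of 1:1 (210 subject/treatment group". The documents give neither event rates for this trial nor baseline-to-visit correlations for laboratory values. Both are assumed below, over a range.

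**The plan's own figure.** The safety sections state none. As a check on the arm size, SAP 2.4 claims "approximately 90% power to detect a difference in HAQ-DI mean change from baseline of 0.24", "assuming that the common standard deviation is 0.72", at a "0.05 two-sided significance level and accounting for a 10% dropout rate". With 210 × 0.9 = 189 evaluable per arm, the standard error is 0.72 × √(2/189) = 0.0741. Then 0.24/0.0741 − 1.96 = 1.28, which gives power of 90.0% (89.8% by noncentral t). The figure reproduces.

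**Adverse-event intervals.** Wald: p1 − p2 ± 1.96 × √(p1(1−p1)/n + p2(1−p2)/n), with n = 210.

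- 0 vs 0: the square root is 0, so the limits are 0.00% to 0.00%.
- 1 vs 0: p1 = 0.476%, standard error 0.475%, limits 0.476% ± 0.931%, that is -0.45% to 1.41%.

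The Miettinen-Nurminen interval keeps every difference d for which the score statistic, with variance evaluated at the rates most likely under d and multiplied by 420/419, is within ±1.96. For 0 vs 0 it has a closed form: d = 3.84/(210 × 419/420 + 3.84) = 3.84/213.3 = 1.80%.

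| Events | Wald | Miettinen-Nurminen |
|---|---|---|
| 0 vs 0 | 0.00% to 0.00% | -1.80% to 1.80% |
| 1 vs 0 | -0.45% to 1.41% | -1.33% to 2.65% |
| 1 vs 1 | -1.32% to 1.32% | -2.21% to 2.21% |
| 3 vs 0 | -0.18% to 3.03% | -0.38% to 4.12% |
| 10 vs 5 | -1.16% to 5.92% | -1.31% to 6.46% |

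The exact 95% upper limit for 0/210 in one arm alone is 1 − 0.025^(1/210) = 1.74%, so a zero-width interval for the difference cannot be right.

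**Coverage of the nominal 95% Wald interval.** This is exact: binomial probabilities summed over both arms, 210 per arm. The last column is the probability that the upper limit falls below the true excess.

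| True rates (assumed) | Coverage | Upper limit too low |
|---|---|---|
| 0.2% vs 0.1% | 46.8% | 53.2% |
| 0.5% vs 0.1% | 71.0% | 29.0% |
| 1% vs 0.5% | 87.0% | 12.2% |
| 2% vs 0.5% | 91.0% | 7.9% |
| 2% vs 1% | 95.1% | 3.9% |
| 5% vs 2% | 94.4% | 3.7% |
| 0.5% vs 0.5% | 98.5% | 0.8% |
| 1% vs 1% | 95.8% | 2.1% |

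The Miettinen-Nurminen interval covers 99.6% at 0.5% vs 0.1% and 93.5% at 2% vs 0.5%.

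**Prior-biologic subgroup.** Biologic-experienced subjects with inadequate response or intolerance are capped at 50%, so that stratum has at most about 105 per arm. If the Wald method is carried over, 0 vs 0 again gives 0% to 0%, against ±3.55% by Miettinen-Nurminen. Wald coverage at 1% vs 0.5% falls to 78.6%.

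**Laboratory model.** Assume equal variance σ² at baseline and follow-up, and correlation ρ.

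- Change score: variance 2σ²(1 − ρ).
- Baseline-adjusted: residual variance σ²(1 − ρ²).
- Ratio: (1 + ρ)/2.

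| ρ (assumed) | Variance ratio | Width ratio | Interval narrower by |
|---|---|---|---|
| 0.5 | 0.75 | 0.866 | 13% |
| 0.7 | 0.85 | 0.922 | 8% |
| 0.8 | 0.90 | 0.949 | 5% |
| 0.9 | 0.95 | 0.975 | 2.5% |

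Simulation gave variance ratios of 0.743 at ρ = 0.5 and 0.857 at ρ = 0.7. Given a chance baseline difference Δ between the arms, the change-score estimate is shifted by −(1 − ρ)Δ, which is half of Δ at ρ = 0.5. ANCOVA removes this shift.

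**The case against.** The best defence is that these intervals decide nothing. SAP section 12 confines formal testing to the primary and ranked efficacy endpoints, and Protocol 7.4 calls the laboratory analysis descriptive. Serious events, deaths and discontinuations are listed individually. Cardiovascular and anaphylactic events are adjudicated blind, and the data monitoring committee sees unblinded safety data about every six months. All of this is true and limits the consequence. It does not make a 95% interval of zero width correct.

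A second argument is that the worst coverage figures mostly restate the 0 vs 0 case, where the reader sees the counts anyway. That is largely right. At 0.2% vs 0.1% essentially all of the 53.2% misses are 0 vs 0 tables, and at 0.5% vs 0.1% they account for 28.3 of the 29.0 points. At 1% vs 0.5%, however, only 4.2 of 13.0 points come from that cell, so the defect is wider. Coverage is also at or above nominal when the true rates are equal, and close to nominal at 2% vs 1%. The shortfall is confined to true rates of about 1% or lower in at least one arm that differ between the arms.

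On the laboratory side, ANOVA of change is unbiased under randomisation, and safety signals are sought mainly through shift tables, threshold counts and the eDISH plot. This stands: that half is a matter of efficiency, not validity.

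Finally, no single score-type interval is uniquely right. Newcombe's has almost the same width, yet at 4 vs 0 it includes zero (-0.23% to 4.79%) while Miettinen-Nurminen (0.09% to 4.80%) and Wald (0.06% to 3.75%) exclude it. That is a reason to name one method before unblinding, not to keep Wald.

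**Conclusion.** The concern holds, with unequal weight on its two parts. The adverse-event interval is wrong as written for sparse categories. It has zero width at 0 vs 0, is less than half the score interval's width at 1 vs 0 (1.86 against 3.98 points), and covers about 47% to 87% in the three assumed rare-event settings of 0.2% vs 0.1%, 0.5% vs 0.1% and 1% vs 0.5%. Most misses understate harm. For common adverse events the choice hardly matters. The laboratory model is valid but gives up roughly 5% to 13% of interval width for correlations of 0.5 to 0.8, and about 2.5% at 0.9.

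The event rates and correlations are assumptions, as is equal laboratory variance at baseline and follow-up. Type I error and the efficacy conclusions are unaffected; what changes is how the safety tables read. The correction should be made.

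**What to change.** - **SAP 9.2.1.1 and 9.2.1.5:** replace the normal-approximation interval by the Miettinen-Nurminen score interval for all differences in the percentage of subjects with adverse events or events of safety interest, and name the method in 9.2.1.5. Using one method throughout avoids choosing by observed count.
- **SAP 9.3.2.1:** replace the ANOVA by ANCOVA with treatment as factor and the baseline value of the same laboratory parameter as covariate.

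The cost is SAP wording and standard SAS options, with no new data and no change to sample size or conduct. Rare-event intervals become wider, which is the intended effect.
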